7.1.5.3.2. Sponsor Responsibility

If a serious unexpected adverse event is believed to be related to the study drug or study procedures, the sponsor will take appropriate steps to notify all investigators participating in sponsored clinical studies of pridopidine and the appropriate competent authorities (and IEC/IRB, as appropriate).

In addition to notifying the investigators and competent authorities (and IEC/IRB, as appropriate), other measures may be required, including:

- altering existing research by modifying the protocol
- discontinuing or suspending the study
- altering the process of informed consent by modifying the existing consent form and informing all study participants of new findings
- modifying listings of expected toxicities to include adverse events newly identified as related to pridopidine

7.1.6. Protocol-Defined Adverse Events for Expedited Reporting

Adverse events of suicidal ideations or attempt should be reported to the sponsor within 24 hours of learning of the event. The corresponding dedicated CRF should be completed, but the events should not be marked as serious unless deemed serious by the investigator. The words “protocol defined adverse event” should be added after the adverse event term. Once the adverse event of suicidal ideation or attempt is received, the subject should be discontinued from the study and referred to a psychiatrist for evaluation and monitoring.

7.1.7. Withdrawal Due to an Adverse Event

Any subject who experiences an adverse event may be withdrawn from the study or from study treatment at any time at the discretion of the investigator. If a subject is withdrawn wholly or in

part because of an adverse event, both the adverse events page and termination page of the CRF will be completed at that time.

In addition, a blood sample will be obtained for the measurement of study drug concentrations. The subject will be monitored at the discretion of the investigator (eg, until the event has resolved or stabilized, until the subject is referred to the care of a health care professional, or until a determination of a cause unrelated to the study drug or study procedure is made). The investigator must inform the clinical project physician (CPP)/clinical leader (CL) as soon as possible of each subject who is being considered for withdrawal due to adverse events. Additional reports must be provided when requested.

If a subject is withdrawn from the study drug for multiple reasons that include adverse events, the termination page of the CRF should indicate that the withdrawal was related to an adverse event. An exception to this requirement will be the occurrence of an adverse event that in the opinion of the investigator is not severe enough to warrant discontinuation but that requires the use of a prohibited medication, thereby requiring discontinuation of the subject. In such a case, the reason for discontinuation would be need to take a prohibited medication, not the adverse event.

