2.3.3. Safety and Tolerability Endpoints

The safety and tolerability endpoints are:

- occurrence of adverse events during the study
- clinical laboratory (serum chemistry, hematology, and urinalysis) test results
- vital signs (blood pressure [BP], respiratory rate, body temperature, and pulse) measurements at each visit
- ECG findings
- physical examination findings, including body weight measurements
- use of concomitant medication during the study

- number (%) of subjects who did not complete the study (end of study)
- number (%) of subjects who did not complete the study due to adverse events

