5.3. Prior and Concomitant Medication or Treatment

Medications administered prior to any study drug administration will be recorded as prior medications and medications administered following the first dose and throughout the study will be recorded as concomitant medication. Any prior or concomitant therapy, medication, or procedure a subject has had within 28 days before study drug administration and up to the end of the study period, including follow-up, will be recorded on the CRF. Generic or trade name, indication, dosage, and dosing start and stop times will be recorded. The sponsor will encode all therapy and medication according to the World Health Organization drug dictionary (WHO Drug).

For healthy subjects, other than study drug, no drug is allowed during the study, except for the occasional use of paracetamol/acetaminophen or ibuprofen. Prohibited medication for HD patients is detailed in Section 5.3.1.

At each clinic visit after the screening visit, the investigator will ask subjects whether they have taken any medications (other than study drug), including OTC medications, vitamins, or herbal or nutritional supplements, since the previous visit. Indication, dosage, and start and end dates should be entered on the CRF.

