8. TOLERABILITY VARIABLES AND ANALYSIS

Subject tolerability assessments (the number [%] of subjects who fail to complete the study, number [%] of subjects who fail to complete the study due to adverse events, and the number of subjects who experience treatment-emergent adverse events) will be summarized by part and cohort in the disposition table.

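### The prohibited-medication exception in Protocol 7.1.7 can understate non-completion due to adverse events, and the SAP does not add the excepted cases back

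*Protocol*

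**What the plan says.** Protocol 2.3.3 lists two separate non-completion endpoints: "number (%) of subjects who did not complete the study (end of study"), for any cause, and "number (%) of subjects who did not complete the study due to adverse events". SAP 1.1.2.3 repeats both. SAP 8 places the "number [%] of subjects who fail to complete the study due to adverse events" in the disposition table, by part and cohort. SAP 5.2 summarises withdrawals by recorded reason and lists them.

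Protocol 7.1.7 governs how the reason is recorded:

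- If an AE is even a partial reason for leaving, the site fills in the AE page as well as the termination page.
- Where there are several reasons and an AE is among them, "the termination page of the CRF should indicate that the withdrawal was related to an adverse event".
- The exception is an event that, in the investigator's opinion, "is not severe enough to warrant discontinuation but that requires the use of a prohibited medication, thereby requiring discontinuation of the subject". For it, "In such a case, the reason for discontinuation would be need to take a prohibited medication, not the adverse event".

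Which medicines count as prohibited depends on the population. For healthy subjects, Protocol 5.3 says that "no drug is allowed during the study, except for the occasional use of paracetamol/acetaminophen or ibuprofen". HD patients have named lists in 5.3.1, and the coagulation list in 5.3.1.5 exempts use to treat an AE.

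**The concern.** In the excepted case the AE starts the chain: without it there is no prohibited medicine, and without the medicine there is no discontinuation. The recorded reason nevertheless moves to a non-AE category. The disposition table is built from recorded reasons, so the recoding passes straight into a named endpoint unless the SAP intervenes, and it does not.

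Safety is a secondary objective and the study is descriptive, so the tabulated count is itself the result. Whether a case is recoded turns on an investigator's severity judgement in an open-label study. The list of disallowed medicines is very wide for healthy subjects, who are to be the majority (Protocol 4.3). The SAP is conservative elsewhere: SAP 7.2 treats missing severity as severe and missing relationship as related. This rule leans the other way.

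**Working it through.** The documents give no rate, precision target or sample-size calculation for this endpoint, so there is no planned figure to reproduce.

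**Step 1. Path of one excepted case through the tables.**

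| Output | Source | Is the case counted? |
|---|---|---|
| Non-completion due to AEs | Protocol 2.3.3; SAP 8 | No, if taken from the recorded reason |
| All-cause non-completion | Protocol 2.3.3; SAP 8 | Yes |
| Withdrawal by reason, and listing | SAP 5.2 | Yes, under prohibited medication |
| AE listing | SAP 7.2 | Yes |
| AE incidence summaries | SAP 7.2 | Yes, unless the event was already present before the first tracer dose |
| Summary of AEs that led to withdrawal | Protocol 9.10.2; SAP 7.2 | Not defined |

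The last row is open because neither document says whether that summary is drawn from the AE page or from the termination page. Protocol 7.1.2 records the action taken with study drug for each AE, separately from the termination reason.

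**Step 2. Direction.** The exception moves cases only from AE to non-AE. No rule in 7.1.7 moves a case the other way. Any error is therefore downward.

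**Step 3. Size per case.** Change in the rate = k/n, for k recoded subjects among n. With k = 1:

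- Cohort of 4 (largest planned cohort size, Protocol 3.1): 1/4 = 25.0 points, so 25% reads as 0%.
- Part B at 15 subjects: 1/15 = 6.7 points.
- Part A at 20 subjects: 1/20 = 5.0 points.
- All 45 enrolled: 1/45 = 2.2 points.

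With k = 0 the change is zero.

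**Step 4. Chance of at least one case.** P = 1 − (1 − p)^n, where p is the probability that a given subject becomes an excepted case. The documents give no value for p. The values below are assumptions chosen to show a range.

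| Assumed p | n = 4 | n = 45 |
|---|---|---|
| 1% | 1 − 0.99^4 = 3.9% | 1 − 0.99^45 = 36% |
| 2% | 1 − 0.98^4 = 7.8% | 1 − 0.98^45 = 60% |
| 5% | 1 − 0.95^4 = 18.5% | 1 − 0.95^45 = 90% |

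The probability that matters is of meeting both conditions of the exception, not merely of needing treatment, so p could lie below this range.

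**Step 5. Which product the case speaks to.** Pridopidine is given once, on day 1 of visit 3. A discontinuation between visits 2 and 3 precedes it, and Part 0 receives none. SAP 3.2 counts the tracer as study drug, so such cases bear on tolerability of the tracer or of study participation. Only cases after the pridopidine dose bear on pridopidine. What remains after that dose is same-day imaging, sampling to 24 hours and a follow-up visit 6 days (±1) after dosing.

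**Step 6. Does the medicine force discontinuation?** 7.1.7 describes it as requiring discontinuation. Protocol 7.1.9 allows case-by-case deviations after an AE and leaves continuation to the investigator in consultation with the sponsor. Protocol 11.1.2 names use of prohibited medication as a possible violation, on which the sponsor may let the subject stay. These sections do not agree.

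**The case against.** The strongest reply is that the exception is explicit, prespecified and narrow. It separates events that warrant withdrawal from removals that follow from the medication rules. It needs two things at once: an event judged insufficient in itself, and a medicine that actually ends participation. Deleting it would label as an AE discontinuation something the investigator thought did not justify one. The single dose also leaves little pridopidine follow-up in which the rule could operate, and every component of the case is visible elsewhere in the output.

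Most of this stands, and it rules out several stronger readings that a reader might infer:

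- *That the endpoint is undercounted as a matter of fact.* It is undercounted only if a case arises, and the documents give no basis for saying that one will.
- *That almost any treated event in a healthy subject is recoded.* The list of disallowed medicines is wide, but 5.3 does not say that taking one ends participation, and 7.1.9 and 11.1.2 allow the subject to continue. An event that itself warrants discontinuation is still coded as an AE.
- *That pridopidine will look better tolerated than it is.* This could apply only to cases after the single dose.
- *That the event disappears from the safety data, or from the summary of events leading to withdrawal.* It stays in the AE listing. Whether it enters that summary is undefined, so exclusion cannot be asserted.

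What the reply does not remove is that, for a subject who is discontinued under the exception, the named endpoint records a departure that began with an AE as if it did not. A reader can rebuild the true count only by linking the disposition, AE and medication listings.

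**Conclusion.** The point holds as a limited one. The exception can understate non-completion due to AEs, neither document adds the excepted cases back, and the error has one direction. The per-case size is 25 points in a cohort of 4 and 2.2 points across 45 enrolled, and the total effect may be zero. The percentage sizes assume full cohorts and planned enrolment; smaller cohorts raise them, and the pooling of cohorts that SAP 4.1 permits lowers them. The conclusion also assumes that the endpoint is programmed from the termination reason. SAP 5.2 and 8 imply this, since both use the disposition table, but do not state it. This is a minor reporting matter in a descriptive study and leaves the sigma-1 occupancy objectives untouched.

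**What to change.** **Preferred.** Add one line to SAP 7.2 and 8. Count as AE-related non-completion every discontinuation in which the prohibited medicine was given to treat an AE, and show these cases in a separate row of the disposition table. The data are already collected: medication indication (Protocol 5.3) and treatment given for each AE (Protocol 7.1.2). The separate row keeps the distinction that 7.1.7 wants. The same line should name the source page for the summary of AEs leading to withdrawal, and should separate cases before the pridopidine dose and in Part 0 from those after it.

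**Alternative.** Delete the exception in 7.1.7, record the AE as the primary reason and record the prohibited medicine as a secondary reason.

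**In either case.** Reconcile 7.1.7 with 7.1.9 and 11.1.2 on whether use of a prohibited medicine ends participation. Which clinical rule should apply is not a matter for this review.

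**Cost.** The preferred route costs a SAP line and one table row. The alternative costs a protocol sentence and a secondary-reason field or completion note on the CRF. The AE-discontinuation figure may be slightly less favourable. The coding change alone does not alter who is treated or discontinued.

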7.1.8. Overdose of Study Drug

Any dose of study drug (whether the investigational product or tracers), whether taken intentionally or unintentionally, in excess of that prescribed must be immediately reported to the sponsor.

7.1.9. Protocol Deviations Because of an Adverse Event

If a subject experiences an adverse event or medical emergency, deviations from the protocol may be allowed on a case-by-case basis. To ensure subject safety, after the event has stabilized or treatment has been administered (or both), the investigator or other physician in attendance must contact the physician identified in the Clinical Study Personnel Contact Information section of this protocol as soon as possible to discuss the situation. The investigator, in consultation with the sponsor, will decide whether the subject should continue to participate in the study.

7.2. Pregnancy

Only male healthy subjects and (optional) HD patients will be enrolled in this study.

All pregnancies of female partners of men participating in the study that occur within 3 months of completion of the study, are to be reported immediately to the physician identified in the Clinical Study Personnel Contact Information section of this protocol, and the investigator must provide the LSO/CRO with the pregnancy form. The process for reporting a pregnancy is the same as that for reporting a serious adverse event but using the pregnancy form (see Section 7.1.5.3).

7.3. Medication Error and Special Situations

Any administration of medication that is not in accordance with the study protocol should be reported on the CRF either as a violation, if it meets the violation criteria specified in the protocol (Section 11.1.2), or as a deviation, in the subjects source documents, regardless of

whether an adverse event occurs as a result. All instances of incorrect medication administration should be categorized on the CRF as “Non-Compliance to investigational medicinal product (IMP)”.

Types of medication errors and special situations:

1. Medication error: Any unintentional error in the prescribing, dispensing, or administration of a medicinal product while in the control of the healthcare professional, subject, or consumer.
2. Overdose: Administration of a quantity of a medicinal product given per administration or cumulatively which is above the maximum recommended dose according to the authorized product information. Clinical judgment should always be applied.
3. Misuse: Situations where the medicinal product is intentionally and inappropriately used not in accordance with the authorized product information.
4. Abuse: Persistent or sporadic, intentional excessive use of medicinal products which is accompanied by harmful physical or psychological effects.
5. Off-label use: Situations where a medicinal product is intentionally used for a medical purpose not in accordance with the authorized product information.
6. Occupational exposure: Exposure to a medicinal product, as a result of one’s professional or non-professional occupation.

7.4. Clinical Laboratory Tests

All clinical laboratory test results outside of the reference range will be judged by the investigator as belonging to one of the following categories:

- abnormal and not clinically significant
- abnormal and clinically significant

A laboratory test result that is judged by the investigator as clinically significant will be recorded on the source documentation, transcribed to the CRF as an adverse event, and monitored as described in Section 7.1.2. An event may include a laboratory or diagnostic test abnormality (once confirmed by repeated testing) that results in the withdrawal of the subject from the study, the temporary or permanent cessation of treatment with study drug or medical treatment, or further diagnostic work-up.

In addition, potentially clinically significant values may be predefined by the sponsor for selected laboratory test variables (see Section 9.10.2) and, if so, will be documented in the statistical analysis plan or other relevant documents (eg, medical monitoring plan or laboratory analysis plan).

7.4.1. Serum Chemistry, Hematology, and Urinalysis

Clinical laboratory tests (serum chemistry, hematology, coagulation, and urinalysis) will be performed at the time points detailed in [Table 1](#). Clinical laboratory tests will be performed using a central laboratory. Specific laboratory tests to be performed are provided in [Table 5](#).

Table 5: Clinical Laboratory Tests

Serum Chemistry	Hematology and Coagulation	Urinalysis
calcium	hemoglobin	protein
phosphorus	hematocrit	glucose
sodium	red blood cell (RBC) count	ketones
potassium	RBC indices	blood (hemoglobin)
magnesium	platelet count	pH
chloride	white blood cell (WBC) count, and differential count and percentage	specific gravity
glucose	– absolute neutrophil count (ANC)	microscopic
blood urea nitrogen (BUN)	– polymorphonuclear leukocytes (neutrophils)	– bacteria
creatinine (including calculation of creatinine clearance using the Cockcroft-Gault formula)	– lymphocytes	– RBCs
cholesterol (low density lipoprotein (LDL)/high density lipoprotein (HDL) /total)	– eosinophils	– WBCs
uric acid	– monocytes	– casts
alanine aminotransferase (ALT)	– basophils	– crystals
aspartate aminotransferase (AST)	– atypical lymphocytes	
lactate dehydrogenase (LDH)	Prothrombin International Normalized Ratio (INR)	
gamma-glutamyl transpeptidase (GGT)	Activated partial Thromboplastin Time (aPTT)	
alkaline phosphatase		
creatine phosphokinase (CPK) - in case of elevated CPK, the MB fraction should be measured		
total protein		
albumin		
total bilirubin		
direct bilirubin		
indirect bilirubin		
prolactin		

7.4.2. Other Clinical Laboratory Tests

At screening, subjects will be tested for HIV-1, HIV-2, HBsAg, and hepatitis C antibody.

7.4.2.1. Urine Drug Screen

A urine drug screen will be performed at screening and on day -1. The drug screen will detect the presence of amphetamines, cocaine, opiates, cannabis, barbiturates, and benzodiazepine. A positive result for any of these drugs or their metabolites, without medical explanation, will preclude the subject from enrollment or continued participation in the study.

7.4.2.2. Corticoid Plasma Levels

Endogenous corticoid plasma levels will be measured on day 1 of visits 2 and 3 (immediately before the tracer injection). The analysis will include measurement of DHEA, progesterone, testosterone, cortisol, and, where feasible, androstanolone, allopregnanolone, pregnenolone.

7.5. Vital Signs

Vital signs (pulse, BP, body temperature, and respiratory rate) will be measured at the time points detailed in [Table 1](#). All vital signs results outside of the reference ranges will be judged by the investigator as belonging to one of the following categories:

- abnormal and not clinically significant
- abnormal and clinically significant

Before pulse and BP are measured, the subject must be in a seated or supine position and resting for at least 5 minutes. (The same position and arm should be used each time vital signs are measured for a given subject.) For any abnormal vital sign finding, the measurement should be repeated as soon as possible. Any vital sign value that is judged by the investigator as a potentially clinically significant change (worsening) from a baseline value will be considered an adverse event, recorded on the source documentation and transcribed onto the CRF, and monitored as described in Section [7.1.2](#).

In addition, potentially clinically significant values may be predefined by the sponsor for selected vital signs (see Section [9.10.2](#)) and, if so, will be documented in the statistical analysis plan or other relevant documents (eg, medical monitoring plan).

When vital signs collection coincides with a pharmacokinetic sample, vital signs will be collected before the pharmacokinetic sample.

7.6. Electrocardiography

A 12-lead ECG will be recorded at the time points detailed in [Table 1](#). A qualified physician will be responsible for interpreting the ECG. Any ECG finding that is judged by the investigator as clinically significant will be considered an adverse event, recorded on the source documentation, transcribed to the CRF, and monitored as described in Section [7.1.2](#).

The 12-lead ECG is to be performed before pridopidine administration; immediately before administration of the tracer (approximately 90 minutes after pridopidine administration), and at the end of the first PET scan (approximately 3.5 hours after pridopidine administration).

When ECG collection coincides with a pharmacokinetic sample, ECG will be collected before the pharmacokinetic sample.

7.7. Physical Examinations

Physical examinations, including height and weight (to be obtained at the screening visit only), will be performed at the time points detailed in [Table 1](#). Any new physical examination finding that is judged by the investigator as clinically significant will be considered an adverse event, recorded on the CRF, and monitored as described in Section [7.1.2](#).

A complete physical examination will be performed at screening and at the follow-up/ET visits only. On other occasions, an abbreviated/symptom-oriented physical examination will be performed.

7.8. Concomitant Medication or Treatment

Use of concomitant medication or treatment will be monitored throughout the study. Details of prohibited medications are found in Section 5.3.

7.9. Assessment of Local Tolerability and Pain

Local tolerability at the injection site of the tracer (eg, pain, erythema, ecchymosis, induration) will be evaluated as part of the standard medical supervision during administration.

